1153 dehydrogenase; T-test; total testosterone; SHBG, sex-hormone binding globulin; LH, luteinizing
1154 hormo33.5.ne; DHEA-S, dehydroepiandrosterone-sulfate; FFA, free-fatty acids; β-HB, beta-
1155 hydroxybutyrate; GLP-1, glucagon-like peptide-1; PYY, peptide-YY; PP, pancreatic polypeptide; I-FABP,
1156 intestinal fatty acid binding protein; LBP, lipopolysaccharide binding protein, PBMC, peripheral blood
1157 mononuclear cells. ²Blood will be sampled seven times during the fractional iron absorption studies
1158 through an indwelling venous catheter for the notated analytes (0, 20, 40, 60, 120, 240, and 360 min) for
1159 a total of 21 blood draws (seven per iron study). A final blood draw will be taken on each of the iron study
1160 mornings (1 per iron study morning; 3 total) through the indwelling venous catheter that is separate from
1161 the seven draws for the iron studies in order to analyze the remaining markers (marked with an x on days
1162 2, 6, and 16) at the same time of day as those measured on the other study mornings when blood draws

1163 occur after an overnight fast (venipuncture). ³A second blood sample will be collected post-exercise for
1164 the notated analytes on days 3, 5, 13, and 15. ⁴Serum, EDTA, LiHep archived blood samples are derived
1165 from the blood draws at each specific time point, and stored in the event certain assays require re-
1166 analysis, or for future analysis if any sample remains. Based on this explanation, the total number of
1167 study blood draws is 42 (iron study days, 8 x 3 = 24; 2 on days 3, 5, 13, and 15, for 8 total draws; and 1
1168 on every other indicated blood draw day, 10 total). Serum and plasma will be archived from each blood
1169 draw. The total volume of blood collected per participant is ≤ ~530 mL.
1170

1171 **Saliva analysis**

1172 Saliva collection is a non-invasive technique with easy achievability that may facilitate sample
1173 collection in austere environments by study volunteers with minimal instruction. The technique
1174 may therefore provide an efficient alternative to using blood and/or fecal collection to monitor
1175 physiological status in Warfighters engaged in SUSOPS or during deployment. However, the
1176 validity of saliva collection as a deployable solution for monitoring physiologic status requires
1177 validation. As such, saliva and blood samples will be collected in tandem. Blood will be

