1178 subjected to mRNA-seq, targeted micro-RNA (see *mRNA, myomiR, and c-myomiR Expression*
1179 below) and metabolomics analyses. Saliva will be subjected to microRNA profiling, ion
1180 abundance measurement and metabolomics analyses. Results will be compared between
1181 sample types, and in relation to the gut microbiome, and cognitive and physical performance
1182 outcomes. In addition to validating the approach, analyses will be undertaken to explore
1183 associations between the salivary microbiome and stress responses.
1184

1185 Saliva samples will be collected on study days 2, 6, 9, 16 and 19 at the same time blood
1186 samples will be collected for mRNA-seq, microRNA-seq and metabolomics assays,
1187 respectively. During saliva collection, a Salivette tube with opaque white cap (SARSTEDT, Inc.)
1188 will be opened; the swab will be removed and placed in the mouth. After 45 seconds (gentle
1189 chewing possible, but not required), the saliva-soaked swab will be returned to the Salivette®
1190 which will be closed with the plug for storage and transport. The expected yield is 0.8-1.4 mL
1191 saliva. A second round of sample collection will occur 30 minutes later following the same
1192 procedure. The tubes will be frozen at -80°C and shipped to USACEHR. Upon receiving the
1193 tubes, the tubes will be centrifuged at room temperature at 1000g for 2 minutes. The first tube
1194 will be used for microRNA sequencing and microbiome shot gun sequencing. The second tube
1195 will be used for metabolomics and targeted proteomics (inflammatory panel of 65 protein
1196 markers will be tested using the Luminex platform).
1197

1198 **Determination of Fractional Iron Absorption**

1199 Stable isotope concentrations in whole blood will be determined by inductively coupled plasma
1200 mass spectrometry (ICP-MS) by the Energy and Environmental Sustainability Laboratory
1201 (EESL) at Pennsylvania State University (PSU) using a fee-for-service contract.
1202

1203 The amount of absorbed iron in circulation will be calculated using isotope dilution as described
1204 previously [70, 99]. Briefly, the amount of absorbed iron circulating in blood will be calculated
1205 based on the amount of stable isotope administered, the amount of stable isotope detected in
1206 the blood, hemoglobin concentration, and blood volume, which will be estimated based on
1207 volunteer height and weight [100]. Isotope dilution will also be used to calculate fractional iron

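### The saliva tube used for metabolomics is taken 30 min after the first tube with no matching blood draw, and chewing is optional and unrecorded, so saliva-blood agreement may be lowered for avoidable reasons

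*Combined protocol and SAP*

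**What the plan says.** Section B5.4, Saliva analysis, presents saliva as a possible field alternative to blood or fecal sampling and says that this use still needs validation. Hence "As such, saliva and blood samples will be collected in tandem". The schedule reads "Saliva samples will be collected on study days 2, 6, 9, 16 and 19 at the same time blood" is drawn for mRNA-seq, microRNA-seq and metabolomics.

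Two swabs are taken. After the first, "A second round of sample collection will occur 30 minutes later following the same" procedure. The first tube "will be used for microRNA sequencing and microbiome shot gun sequencing. The second tube" "will be used for metabolomics and targeted proteomics (inflammatory panel of 65 protein" markers. Each swab stays in the mouth for 45 seconds, with gentle chewing "chewing possible, but not required". The expected yield is 0.8-1.4 mL.

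The comparison with blood is given only in general terms: "abundance measurement and metabolomics analyses. Results will be compared between" sample types. No agreement statistic or limit is named.

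Table 1 marks blood metabolomics and mRNA-seq with one x on each of days 2, 6, 9, 16 and 19. It has no microRNA-seq row. Its two blood microRNA rows (c-myomiRNA and Exo miRNA) fall on days 3, 5, 6, 13, 15 and 16.

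**The concern.** The point of paired sampling is that any disagreement between saliva and blood reflects the two fluids and not the circumstances of collection. Here the tube that coincides with the blood, on the natural reading, is used for sequencing. The tube used for metabolomics, for which Table 1 does schedule a blood assay of the same kind on every saliva day, comes half an hour later. The section does not restrict eating or drinking in between.

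Optional chewing adds a second uncontrolled factor. Saliva from men who chew and men who do not will be mixed, and one man may differ from day to day. Because the section does not ask for chewing, volume or flow to be recorded, the analyst could neither adjust for it nor show that it did not matter.

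At stake is a fair test of saliva as a substitute for blood, together with some precision in the saliva ion, metabolite and protein data. A poor saliva-blood correlation could be blamed on saliva when part of it came from the collection rule. This cannot be repaired after the samples are taken.

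**Working it through.** **1. Is there a blood draw for the later tube?** Inputs are Table 1 and its footnotes. There are 17 draw days.
- Iron study days 2, 6 and 16: 7 timed draws plus 1 separate draw for the markers shown with an x, so 3 × 8 = 24.
- Days 3, 5, 13 and 15: 2 draws each, so 4 × 2 = 8.
- The other 10 days: 1 draw each, so 10.
- Total: 24 + 8 + 10 = 42, which reproduces the plan's figure.

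No draw is left over. Days 9 and 19 have one draw each. On days 2, 6 and 16 metabolomics belongs to the single separate draw, and the timed iron draws (0, 20, 40, 60, 120, 240 and 360 min) include none at 30 min. If the first swab coincides with the blood, the metabolomics swab is 30 min late on all five days.

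**2. Which saliva assay has a blood counterpart?**
- Metabolomics: blood on days 2, 6, 9, 16 and 19, so 5 of 5 saliva days. With 15 completers (B5.2.2) that is up to 15 × 5 = 75 pairs.
- microRNA, by Table 1: blood overlaps saliva only on days 6 and 16, so up to 15 × 2 = 30 pairs. The Saliva analysis text instead names blood microRNA-seq on all five days. The two places disagree.
- Microbiome: no blood counterpart.
- 65-protein panel: no such row in Table 1 and no blood protein panel in the Saliva analysis text. Blood has single markers such as IL-6 and hs-CRP, and blood proteomics is named only in the systems biology background in B2.
- Ion abundance: listed for saliva, but not assigned to either tube.

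**3. Is flow handled elsewhere?** In B5.3, Assessment of mucosal immunity, the sIgA swabs are timed (3 min for the first) and salivary flow rate is determined. Those swabs are a different device, taken at baseline and on SUSOPS mornings, so not on days 9 and 19. Nothing says that their flow data will be applied to the tubes discussed here.

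**4. How large could the loss be?** The documents give no within-man variance, drift or flow effect, so the size can only be illustrated. Let R be the share of saliva variance not due to timing or flow, and assume that the remainder is unrelated to the blood level. Then observed r = true r × √R.

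| Assumed R | True r = 0.7 | True r = 0.9 |
|---|---|---|
| 0.95 | 0.68 | 0.88 |
| 0.80 | 0.63 | 0.80 |
| 0.50 | 0.49 | 0.64 |

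The loss is trivial at the top of the table and would change the conclusion at the bottom. The documents do not say which row applies.

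**The case against.** **The lag may not matter.** The saliva days are 3 to 7 days apart and span baseline, the end of a 72-h SUSOPS and recovery. Differences that persist over such periods are untouched by half an hour, and the blood draws are fasted and matched for time of day. This stands, and it limits the claim. A reader might infer that a factor such as exp(-30/τ), which gives 0.61, 0.78 or 0.88 for assumed τ of 60, 120 or 240 min, caps the whole within-man correlation. It would bear only on the fast-varying part of the signal, whose share is unknown.

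**Reassigning the tubes only moves the lag.** If blood microRNA-seq is run on all five days, as the Saliva analysis text says, this is largely right. If Table 1 governs, metabolomics has more to gain. So the reassignment depends on reconciling the two.

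**The wording could pair each tube with its own blood sample.** The sentence ends with a distributive adverb that allows this reading, but the single draw per day in Table 1 does not support it.

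**Intake in the gap is speculative.** Men live in the chambers on days 2, 6 and 16 and eat only staff-provided food during the SUSOPS phases (C1.3). That governs what they eat, not when. Days 9 and 19 fall in recovery, on an ad libitum diet. Nothing shows that intake will occur; nothing prevents it.

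**Later processing may help.** B5.8.2 plans checks for non-biological confounding, with correction and normalization where required. An unrecorded chewing status or volume cannot be entered in such a check.

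**Optional chewing suits field use.** The section values collection with minimal instruction. A single rule is no harder to give than an optional one.

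**Conclusion.** The point holds as a minor, cheap improvement. The text and Table 1 establish three things: the metabolomics swab is 30 min after the first, no blood draw matches it, and chewing is unstandardized with no volume or flow recorded. This rests on one reading, that the first swab is the one taken with the blood, which the plan should state outright. The effect on saliva-blood agreement for metabolomics, and on variation in saliva ions, metabolites and proteins, is possible but not quantified. It concerns an exploratory part of secondary objective 5.

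Three stronger readings are not supported.
- **A diet effect created by the lag.** The lag is the same at every visit, so it does not by itself bias saliva comparisons between phases. Chewing or intake would have to differ by phase, and nothing shows that they will.
- **A protein panel mistimed against its blood reference.** No blood comparator for that panel is specified, so the firm timing mismatch is for metabolomics only.
- **Dilution large enough to mimic an altered analyte.** The yield of 0.8-1.4 mL in 45 s (0.75 min) works out at 0.8/0.75 = 1.07 to 1.4/0.75 = 1.87 mL/min. Calling that a stimulated rate, predicting a shortfall in men who do not chew, or setting dilution against the 1.5-fold criterion in B5.8.2 all need an unstimulated flow that the documents do not give. The stated yield is for a procedure in which chewing is optional, and the criterion also requires P < 0.05.

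**What to change.** In B5.4, Saliva analysis:
1. Replace the optional chewing instruction with one rule (all chew or none chew) and one fixed collection time, used at every session.
2. Allow nothing by mouth from the blood draw until the second swab is finished.
3. Weigh each tube and record the clock time of each swab and of the blood draw, so that collected volume can be used as a covariate.
4. State which swab coincides with the blood draw. Reconcile Table 1 (blood microRNA overlapping saliva on days 6 and 16 only) with the text (blood microRNA-seq on all five days). If Table 1 holds, assign the swab taken with the blood to metabolomics.

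The cost is a few sentences, tube labels and a weighing step, with no extra sample or assay. There are two small downsides: under step 4 saliva microRNA and microbiome would come from the later swab, and a no-chew rule may need a longer collection time.

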831 $\dot{V}O_{2peak}$. Volunteers will begin with a 5 min warm-up at 50% $\dot{V}O_{2peak}$ before beginning the
832 protocol. After a warm-up period, the cycle ergometer protocol is comprised of repeated periods
833 of 2 min of work at $80 \pm 5\% \dot{V}O_{2peak}$ followed by 2 min of recovery at $50 \pm 5\% \dot{V}O_{2peak}$. The
834 protocol will last approximately 50-min (12 work:rest cycles). To ensure familiarity with the
835 testing procedures, volunteers will perform one practice session during the baseline pre-study
836 period. Volunteers will be permitted to consume water *ad libitum* during the protocol.

837

838 After completing the glycogen depletion protocol, volunteers will be fed a controlled diet
839 prescribed to maintain energy balance and provide at least 6.0 g carbohydrate $\cdot kg^{-1} \cdot d^{-1}$ (~55-
840 60% of total energy consumed) to ensure adequate glycogen repletion and homogeneous
841 glycogen levels within and across volunteers between SUSOPS phases (BAL and NEG BAL).
842 All food and beverages (except water) will be prepared and provided by study dietitians and
843 consist largely of military combat ration and supplemental food items.

844

845 **Determination of Fractional Iron Absorption**

846 Volunteers will undergo three acute fractional iron absorption studies (Iron Studies 1, 2, and 3).
847 The studies will occur on days 2, 6, and 16 in the morning (~0000 h) after an 8 h fast. The iron
848 studies on days 6 and 16 will occur ~3 h after completing the last exercise bout of the SUSOPS
849 to correspond to peak hepcidin responses to exercise. An indwelling 18 gauge intravenous
850 catheter will be placed in the antecubital fossa (or distally) and a baseline blood sample will be
851 drawn before consuming the iron isotope (0 min). Volunteers will then consume a 300 mL drink
852 containing 3.8 mg iron (representative of dietary iron in an iron-rich meal) as isotopically labeled
853 $^{54}FeSO_4$, $^{57}FeSO_4$, or $^{58}FeSO_4$ (Trace Sciences International). Venous blood samples will be
854 collected at 20, 40, 60, 120, 240, and 360 min-post iron loading [70] to assess the effects of a
855 transient exercise-induced increase in IL-6 (and hepcidin) on the appearance of absorbed iron
856 in blood.

857

858 **Percutaneous Muscle Biopsy of the Vastus Lateralis**

859 Percutaneous muscle biopsies will be obtained from the vastus lateralis using a 5 mm

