1208 incorporation into red blood cells after administration of the stable isotope and assuming 80%
1209 incorporation [70].
1210

1211 An example calculation using ⁵⁴Fe tracer and endogenous concentrations of ⁵⁶Fe is included
1212 below:
1213

$${}^{54}\text{Fe}_{\text{inc}} = \frac{\left(\frac{{}^{54}\text{Fe}}{{}^{56}\text{Fe}_{\text{enr}}} - \frac{{}^{54}\text{Fe}}{{}^{56}\text{Fe}_{\text{base}}} \right) \text{Fe}_{\text{circ}} \cdot \text{NA}_{54}}{\frac{{}^{54}\text{Fe}}{{}^{56}\text{Fe}_{\text{base}}}}$$

- 1214
1215 ${}^{54}\text{Fe}_{\text{inc}}$ = quantity of ${}^{54}\text{Fe}$ incorporated into red blood cells
1216 ${}^{54}\text{Fe}/{}^{56}\text{Fe}_{\text{enr}}$ = enriched isotope ratio
1217 ${}^{54}\text{Fe}/{}^{56}\text{Fe}_{\text{base}}$ = baseline isotope ratio
1218 Fe_{circ} = total circulating iron
1219 NA_{54} = natural abundance of ${}^{54}\text{Fe}$

1220

1221 **Muscle Glycogen**

- 1222 Approximately 20 mg of muscle from each muscle biopsy will be dehydrated in a freeze dryer.
1223 Samples will then be ground to powder and visible connective tissue will be removed.
1224 Powdered muscle will be placed in 500 μl 2 N HCl. Samples will then be placed in an incubator
1225 for 120 min at 100°C. Following incubation samples will be neutralized with 1500 μl 0.67 N
1226 NaOH. Muscle glycogen will be in solution at this point. Glycogen will be quantified by a
1227 fluorometric assay (Sigma-Aldrich, St. Louis, MO, USA or equivalent). Muscle glycogen will be
1228 quantified to determine the contribution of endogenous carbohydrate availability on inflammation
1229 in response to SUSUPS BAL and NEG BAL.

1230

1231 **mRNA, myomiR, and c-myomiR Expression**

- 1232 Total RNA will be isolated from approximately 25 mg of muscle using a mirVana™ miRNA
1233 isolation kit (Invitrogen, Carlsbad, CA, USA) or equivalent. Quantity and quality of RNA will be
1234 assessed using a Nanodrop ND-1000 spectrophotometer (Nanodrop, Wilmington, DE, USA).
1235 Equal amounts of total RNA will be synthesized into cDNA for analysis of mRNA (iScript™
1236 Advanced cDNA Synthesis Kit; Bio-Rad or equivalent) and a TaqMan® microRNA RT kit
1237 (Applied Biosystems, Foster City, CA, USA) or equivalent. Individual primers will be used to
1238 determine the mRNA expression of known muscle inflammatory, anabolic, proteolytic,
1239 myogenic, and metabolic markers susceptible to stress, to include but not limited to, TNF- α ,

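### Whole blood is a poor assay matrix for the 0–360 min iron tracer series; serum or plasma from the same draws would give a far larger signal

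*Combined protocol and SAP*

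**What the plan says.** Section B5.3 (Determination of Fractional Iron Absorption) gives a drink "containing 3.8 mg iron (representative of dietary iron in an iron-rich meal) as isotopically labeled" ferrous sulfate in each of three studies. After a 0 min sample, blood is "collected at 20, 40, 60, 120, 240, and 360 min-post iron loading". The stated purpose is to see the effect of a "transient exercise-induced increase in IL-6 (and hepcidin) on the appearance of absorbed iron" in blood.

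Section B5.4, under the same title, names one matrix for the isotope assay: "Stable isotope concentrations in whole blood will be determined by inductively coupled plasma" mass spectrometry at a contract laboratory. Absorbed iron in circulation is worked out from the dose, the isotope found in "the blood, hemoglobin concentration, and blood volume, which will be estimated based on" height and weight. The one formula printed gives tracer incorporated into red cells and scales to "total circulating iron" and the isotope's natural abundance. Red-cell incorporation is assumed to be 80%.

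Table 1 schedules seven tracer/tracee samples on each of days 2, 6 and 16, and one on every other listed draw day up to day 22. It lists eight serum archive samples on each iron-study day, and its footnote adds: "Serum and plasma will be archived from each blood" draw. No serum or plasma tracer assay is named.

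The isotope is fixed by study: 54Fe at baseline (day 2), 57Fe after SUSOPS 1 (day 6), 58Fe after SUSOPS 2 (day 16). Fractional iron absorption appears in both main objectives (B4), and B5.8.2 analyses iron absorption under Primary Objectives. The plan states neither the isotope-ratio precision nor whether the endpoint is the 6 h curve or red-cell incorporation.

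**The concern.** In the first hours after an oral dose, absorbed iron should be mainly in plasma or on its way to the marrow, and not yet in red cells. Whole blood mixes that small amount with all the iron in haemoglobin. The 6 h series is therefore paired with a matrix and a pool calculation that belong to a later, different measure.

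If the assay is not precise enough, the early curves will be largely noise. They will also be unequally noisy, because the three isotopes have different natural backgrounds. The weakest signal falls on the baseline study, against which both SUSOPS periods are compared.

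**Working it through.** The plan gives no dilution factor, expected enrichment or assay precision, so there is no figure of its own to reproduce.

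**Inputs from the plan.** Dose 3.8 mg of one isotope (B5.3); haemoglobin at least 13 g/dL (B5.2.4); the ratio formula and 80% incorporation (B5.4); 15 completers (B5.2.2).

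**Assumed inputs.** Haemoglobin 15 g/dL (13–17); haematocrit 0.45 (0.40–0.50); serum iron 100 µg/dL (60–170); 3.47 mg iron per g haemoglobin (3.4 as the alternative); blood volume 5.5 L (5.0–6.4); natural abundances 5.845% (54Fe), 2.119% (57Fe) and 0.282% (58Fe); ratio precision 0.01–0.5% RSD.

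**Step 1, dilution.**
- Whole-blood iron: 15 × 10 × 5.5 × 3.47 = 2863 mg.
- Plasma iron: 1 mg/L × 5.5 L × 0.55 = 3.0 mg.
- Dilution: (2863 + 3.0) / 3.0, about 947-fold.
- Low end (haemoglobin 13, haematocrit 0.40, serum iron 170, 3.4 mg/g): 442 / 1.02 + 1 = 434.
- High end (haemoglobin 17, haematocrit 0.50, serum iron 60, 3.47 mg/g): 589.9 / 0.30 + 1 = 1967.

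**Step 2, expected signal.** Rearranging the plan's formula:

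relative rise in ratio = tracer in circulation / (iron pool × natural abundance), with tracer mass multiplied by 55.845 / isotope mass to put it on a molar basis.

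Example, 54Fe with 5% of the dose circulating: 0.05 × 3.8 × (55.845 / 53.94) / (2863 × 0.05845) = 0.118%. In plasma the same tracer gives 0.197 / (3.025 × 0.05845) = 111%.

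| Share of dose in circulation | Matrix | 54Fe | 57Fe | 58Fe |
|---|---|---|---|---|
| 1% | whole blood | 0.024% | 0.061% | 0.45% |
| 5% | whole blood | 0.12% | 0.31% | 2.3% |
| 10% | whole blood | 0.24% | 0.61% | 4.5% |
| 5% | serum or plasma | 111% | 291% | 2147% |

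From haemoglobin 17 with 6.4 L to haemoglobin 13 with 5.0 L, the whole-blood rises at 10% of the dose run 0.18–0.30%, 0.47–0.78% and 3.4–5.8%. For equal tracer mass, the 54Fe signal is 5.845 / 2.119 = 2.8 times weaker than 57Fe and 5.845 / 0.282 = 20.7 times weaker than 58Fe.

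**Step 3, smallest detectable share of the dose in whole blood, one man at one time.** Limit = 3 × √2 × RSD, for the difference of two ratios.

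| RSD | Limit | 54Fe | 57Fe | 58Fe |
|---|---|---|---|---|
| 0.5% | 2.12% | 90% | 35% | 4.7% |
| 0.1% | 0.42% | 18% | 6.9% | 0.9% |
| 0.01% | 0.042% | 1.8% | 0.7% | 0.09% |

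In serum or plasma at 0.1% RSD, the 54Fe figure falls from 18% to about 0.02%.

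**Step 4, late red-cell signal for 54Fe.** At 10% absorption and 80% incorporation: 3.8 × 0.10 × 0.80 / (2863 × 0.0585) = 0.18% (0.19% with the molar correction). At 20% absorption it is 0.36%. Both lie below the 0.42% single-man limit at 0.1% RSD and well above the 0.042% limit at 0.01%.

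**The case against.** A reader might infer that the early curve cannot be resolved at all. The documents do not support that. The verdict turns on a ratio precision they do not give, and at 0.01% RSD whole blood would serve for all three isotopes from about 2% of the dose. Even at 0.1–0.5% RSD, 58Fe is detectable from about 1–5%. The limits in step 3 are also per man. Counting assay error only, a mean over 15 men tightens the limit by √15 = 3.9, so at 0.1% RSD it is 0.42 / 3.9 = 0.11%, and a mean 54Fe rise of 0.12% just clears it. At 0.5% RSD it does not (2.12 / 3.9 = 0.55%).

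A reader might also infer that the primary iron-absorption comparison fails. That does not follow either. The plan never makes the 6 h curve the endpoint, and its only printed formula is for red-cell incorporation. The SUSOPS doses are swallowed about 3 h after exercise, so later incorporation of that dose reflects absorption under those conditions whenever blood is drawn. Table 1 also marks tracer samples on the later draw days. This objection stands, with two limits: the late 54Fe change is itself small, and follow-up to day 22 is 20, 16 and 6 days for Iron Studies 1, 2 and 3, with no day named for the incorporation measure.

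Nor does fixing isotope by study bias the BAL versus NEG BAL contrast in itself, since diet order is randomised. Only the baseline contrast always sets 54Fe against the other two.

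Finally, the calculation is referred to cited isotope studies that were not available here, so a plasma method for early samples may be intended. Archived serum might also rescue the curve. But the plan's own text names whole blood, and archives serve later analysis only if sample is left.

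**Conclusion.** The point holds in a limited form. Whole blood suits red-cell incorporation and is poorly matched to the 0–360 min appearance series, where it weakens the tracer signal about 430- to 1970-fold relative to serum or plasma from the same draws. At an assumed 0.1–0.5% RSD, an individual baseline 54Fe curve is lost or nearly so, 57Fe is marginal and 58Fe is measurable. At about 0.01% RSD the problem largely disappears.

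What is at risk is the early curve, and with it the stated purpose of the serial sampling. The wider iron-absorption comparison may survive on the late red-cell measure. The size rests on assumed haemoglobin, haematocrit, serum iron, blood volume and natural abundances, on the share of the dose circulating, and above all on the unstated precision. The direction does not depend on the exact values. This is an inexpensive improvement to an outcome named in both main objectives, not a defect that invalidates the trial.

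**What to change.** In B5.4:
- Specify serum or plasma from the existing draws as the matrix for the 0–360 min tracer:tracee samples, and reserve volume for it. Serum is the natural choice, since Table 1 lists a serum archive sample for each of the eight draws on those days.
- Compute the early measure from plasma iron and plasma volume, or as a tracer AUC. Table 1 already schedules iron at all seven times.
- Keep whole blood for late red-cell incorporation.
- State the required isotope-ratio precision, and say which measure is the iron-absorption endpoint.

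As a secondary option, rotate the isotopes across Iron Studies 1–3, so that the baseline contrast is not always 54Fe against 57Fe or 58Fe. That has to be settled before dosing.

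The cost is a change to the assay contract, serum or plasma preparation, and somewhat more serum or plasma per time point. No extra draws are needed.
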